ICE=intercurrent event; MAR=missing at random; MNAR=missing not at random.

For ICEs that were not foreseen at the time of writing the protocol and that require the use of the hypothetical strategy, classification as MAR/MNAR will be done in a blinded manner on a case-by-case basis prior to database lock for efficacy and will be documented in a dedicated document. Also, the classification above will be revisited in a blinded manner before database lock for efficacy and will be documented in the same document.

The purpose of this estimand is to evaluate the efficacy of TV-44749 when patients adhere to treatment, while patients who used any prohibited antipsychotic medications or withdrew from the study due to disease progression or lack of efficacy are regarded from that withdrawal time point as behaving like patients randomized to the placebo arm. This also applies to the “other efficacy estimand” (Section 3.2.2).

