4. STUDY DESIGN

4.1. General Study Design and Study Schematic Diagram

This is a Phase 3, multinational, multicenter, randomized, double-blind, parallel-group, placebo-controlled study with an open-label, long-term safety phase to evaluate the efficacy, safety, and tolerability of olanzapine for extended-release injectable suspension (TV-44749) for sc use as treatment of adult patients with schizophrenia.

The study will be composed of 2 periods ([Figure 1](#)): Period 1 (the double-blind, placebo-controlled, efficacy and safety period [acute treatment phase]) and Period 2 (open-label safety period [long-term safety phase]). For each patient, the duration of Period 1 will be 8 weeks, and the duration of Period 2 will be up to 48 weeks.

Patients will be randomized to the 8-week efficacy and safety period (acute treatment phase; Period 1) to 1 of 3 active treatment groups (low [318 mg q1m], medium [425 mg q1m], or high dose [531 mg q1m]) or the placebo group in a 1:1:1:1 ratio.

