Period 2 will be open-label and will not include a placebo group. Period 1 will remain blinded to the Sponsor, the site staff, and the study participants until database lock for Period 1. In order to maintain the blind in Period 1, all patients will be randomized again between Period 1 and Period 2; patients who were previously assigned to the active treatment groups will retain their Period 1 treatment assignment (the re-randomization of patients in the TV-44749 groups is being done only to maintain blinding of Period 1, and de facto is a deterministic assignment and not randomization), and patients who were previously assigned to the placebo group will be randomized to one of the active treatment groups in a 1:1:1 ratio. Revealing of the treatment assignment in Period 2 will be performed only after completion and reporting of the relevant study procedures related to assessment of efficacy and safety endpoints in Period 1 ([Section 6.9.1](#)), on a patient-by-patient basis. The revealing of the Period 2 treatment assignment will be performed after week 8 (visit 11) by the authorized site staff according to a process predefined in the relevant study plans, provided that all requirements stipulated in this process were met. Therefore, the dosing at week 8, although assigned to Period 2, will be handled in a blinded manner by all parties, similarly to the dosing in Period 1. The sites are encouraged to complete the revealing of the treatment assignment procedure before IMP administration in week 12 (visit 12).

During the conduct of this study, an Independent Data Monitoring Committee (IDMC) will review accumulated unblinded safety, pharmacokinetic, and efficacy data on a regular basis, as detailed in the IDMC charter, to evaluate the safety of the product for the purpose of ensuring the continuing safety of the study patients and overseeing study conduct issues, as applicable.

Once all patients completed Period 1, and Period 2 is ongoing, an analysis of the full efficacy data will be performed.

Refer to [Section 6.7.1](#) for a description of allowed concomitant medications (including rescue medications [[Section 6.7.1.1](#)] and antidepressants and/or mood stabilizers [[Section 6.7.1.2](#)]).

Screening (up to 8 days Prior to Randomization to Period 1):

Patients will undergo screening procedures and assessments up to 8 days prior to randomization to Period 1. Patients will provide informed consent at the screening visit before any study-related

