Note: Patients who do not meet RDQ criteria, but in the opinion of the investigator show sufficient clinical stabilization for transition to Period 2 and may benefit from continuation of participation in the study, may continue to Period 2 as inpatients for up to an additional 8 weeks. For such patients, RDQ can be assessed periodically according to investigator discretion; if RDQ criteria are not met by the end of the additional 8-week hospitalization period (week 16), then the patient will be discontinued from study treatment and will be asked to complete ET and FU visits.

Visit 11 (week 8) will be the last visit of Period 1 and the first visit in Period 2. In order to maintain the blind in Period 1, all patients will be randomized again between Period 1 and Period 2; patients who were previously assigned to the active treatment groups will retain their Period 1 treatment assignment (the re-randomization of patients in the TV-44749 groups is being done only to maintain blinding of Period 1, and de facto is a deterministic assignment and not randomization), and patients who were previously assigned to the placebo group will be randomized to one of the active treatment groups in a 1:1:1 ratio. The treatment with TV-44749 at this visit will be assigned to Period 2 and will be performed according to the re-randomization treatment assignment. Scales and questionnaires and other assessments will be completed only once. Revealing of the treatment assignment in Period 2 will be performed only after completion and reporting of the relevant study procedures related to assessment of efficacy and safety endpoints in Period 1 (Section 6.9.1), on a patient-by-patient basis. The revealing of the Period 2 treatment assignment will be performed after week 8 (visit 11) by the authorized site staff according to a process predefined in the relevant study plans, provided that all requirements stipulated in this process were met. Therefore, the dosing at week 8, although assigned to Period 2, will be handled in a blinded manner by all parties, similarly to the dosing in Period 1. The sites are encouraged to complete the revealing of the treatment assignment procedure before IMP administration in week 12 (visit 12).

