6.9.3. Discontinuation of the Placebo Treatment Group

After approximately 440 patients complete the week 8 visit, depending on the need for additional data on exposure or safety, the placebo treatment group will be discontinued and additional patients may be randomized to the study (ie, to Period 1) to the TV-44749 treatment groups only. The patients randomized to the study from that time point will not be included in the primary efficacy analyses, as there will be no concurrent placebo group. The sponsor will notify the sites and the IDMC once the placebo treatment group is discontinued, and new patients from that time point will sign an updated ICF reflecting the actual available treatment groups.

Once all patients who were still ongoing in Period 1 at the time of the placebo group discontinuation will either complete or early terminate from Period 1, and are randomized into Period 2 (if applicable), randomization into Period 2 will no longer be performed, as at that point, all patients in Period 1 will be assigned to TV-44749 treatment groups and will continue their treatment assignment in Period 2 as well.

Period 1 will remain blinded to the Sponsor, the site staff, and the study participants until database lock for efficacy, including for patients randomized after the discontinuation of the placebo treatment group as long as they are still in Period 1. After the data are locked for the purpose of the Period 1 efficacy analyses, the study may continue in an unblinded manner.

Period 1 efficacy data collected from patients randomized after discontinuation of the placebo treatment group will not be included in the primary analysis. Therefore, revealing of Period 1 treatment assignment (ie, since patients will be continuing their treatment assignment in Period 2) for patients who were randomized to the study after discontinuation of the placebo treatment group will not be considered unblinding.

6.9.4. Treatment of Study Participants Following the Outcome of Primary Efficacy Analysis Availability

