2. STUDY DESIGN

2.1. General Design

This is a Phase 3, multinational, multicenter, randomized, double-blind, -parallel group, placebo-controlled study with an open-label, long-term safety phase to evaluate the efficacy, safety, and tolerability of olanzapine for extended release- injectable suspension (TV-44749) for subcutaneous (sc) use as treatment of adult patients with schizophrenia.

The study will be composed of 2 periods ([Figure 1](#)): Period 1 (the double-blind, placebo controlled, efficacy and safety period [acute treatment phase]) and Period 2 (open-label safety period [long-term safety phase]). For each patient, the duration of Period 1 will be 8 weeks, and the duration of Period 2 will be up to 48 weeks-.

Patients will be randomized to the 8-week efficacy and safety period (acute treatment phase; Period 1) to 1 of 3 active treatment groups (low dose [318 mg q1m], medium dose [425 mg q1m], or high dose [531 mg q1m]) or the placebo group in a 1:1:1:1 ratio.

Period 2 will be open-label and will not include a placebo group. Period 1 will remain blinded until database lock for Period 1. In order to maintain the masking of Period 1, all patients will be randomized again between Period 1 and Period 2; patients who were previously assigned to the active treatment groups will retain their Period 1 treatment assignment (the re-randomization of patients in the TV-44749 groups is being done only to maintain blinding of Period 1, and de facto is a deterministic assignment and not randomization), and patients who were previously assigned to the placebo group will be randomized to one of the active treatment groups in a 1:1:1 ratio. Revealing of the treatment assignment in Period 2 will be performed only after completion and reporting of the relevant study procedures related to assessment of efficacy and safety endpoints in Period 1 (for more detail see Section 6.9.1 in the protocol), on a patient-by-patient basis. The revealing of the Period 2 treatment assignment will be performed after week 8 (Visit 11) by authorized site staff according to a process predefined in the relevant study plans, provided that all requirements stipulated in this process were met. Therefore, the dosing at week 8, although assigned to Period 2, will be handled in a blinded manner by all parties, similarly to the dosing in Period 1. The sites are encouraged to complete the revealing of the treatment assignment procedure before IMP administration in week 12 (Visit 12).

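### Revealing a patient's Period 2 dose before the Period 1 lock rules out two of the four Period 1 arms, so the stated Period 1 blind does not hold for dose

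*Protocol*

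**What the plan says.** Protocol 4.1 states that "Period 1 will remain blinded to the Sponsor, the site staff, and the study participants until database lock for Period 1". Protocol 6.9 repeats this, and SAP 2.1 and 2.2 carry it in shorter form: "Period 1 will remain blinded until database lock for Period 1".

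The same section of the protocol describes the move into Period 2. Everyone is nominally randomized again, but "patients who were previously assigned to the active treatment groups will retain their Period 1 treatment assignment"; for them the step "de facto is a deterministic assignment and not randomization". By contrast, "patients who were previously assigned to the placebo group will be randomized to one of the active treatment groups in a 1:1:1 ratio". The week 8 dose is given blinded. Authorized site staff then reveal the Period 2 assignment for each patient, once that patient's Period 1 procedures are done and reported, and sites are encouraged to do so before the week 12 dose. Nothing ties the reveal to the Period 1 lock.

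Some decisions remain open until that lock. Under Protocol 3.2.1, intercurrent events not foreseen are classified case by case without knowledge of treatment, and "the classification above will be revisited in a blinded manner before database lock for efficacy". SAP 1.2.1 and 5.7 place this work in a data review meeting before unblinding.

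**The concern.** The re-randomization is there to protect the Period 1 blind, but it can hide only whether a patient was on placebo or on the revealed dose. It cannot hide which dose an active patient had, because no active patient changes dose on entering Period 2. Anyone who sees the Period 2 dose knows that the patient's Period 1 arm was one of two, not one of four.

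What is at stake is whether pre-lock decisions can accurately be called blinded. Period 2 is open-label and its dose changes are recorded in the CRF (Protocol 4.1). Neither document says that these data are kept from the sponsor team that reviews intercurrent events and amends the SAP before lock. The protocol does take such care elsewhere: post-dose prolactin is withheld from sponsor and sites until the Period 1 lock (Protocol 6.10.2 and 8.4.2.3).

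**Working it through.** The documents state no probability for this inference, so there is no figure of theirs to reproduce.

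**Inputs**
- Period 1 allocation to three doses "or the placebo group in a 1:1:1:1 ratio" (Protocol 4.1), so 1/4 per arm.
- Active patients: same dose in Period 2 with probability 1. Placebo patients: 1/3 to each dose (Protocol 4.1).
- About 640 randomized and about 440 completing week 8 (Protocol 10.1; SAP 2.5): 440/640 = 68.75% overall. The assumed early-termination rate is redacted, and no rate by arm is given.

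**Step 1: exclusion.** If dose d is revealed, the patient cannot have been on either of the other two doses in Period 1. Their probability is 0 without any further assumption.

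**Step 2: equal entry.** By Bayes' rule,
P(Period 1 = d | Period 2 = d) = (1/4) / (1/4 + 1/4 × 1/3) = (1/4) / (1/3) = 75%.
Placebo has the remaining 25%. Before the reveal each arm had 25%.

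**Step 3: unequal entry.** Let k be the placebo rate of entry into Period 2 divided by the rate for dose d. The probability becomes 1/(1 + k/3). As an assumption, take 68.75% as the overall entry rate and give the three doses a common rate, (4 × 0.6875 − placebo rate)/3:

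| Placebo entry (assumed) | Active entry | k | P(same dose) |
|---|---|---|---|
| 50% | 75.0% | 0.667 | 81.8% |
| 55% | 73.3% | 0.750 | 80.0% |
| 65% | 70.0% | 0.929 | 76.4% |
| 68.75% | 68.75% | 1.000 | 75.0% |
| 75% | 66.7% | 1.125 | 72.7% |
| 80% | 65.0% | 1.231 | 70.9% |

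**Step 4: active versus placebo.** Under equal entry, P(placebo) is 25% before and after the reveal. With unequal entry by dose it moves little. At assumed entry rates of 60%, 70% and 75% for low, medium and high dose and 65% for placebo, P(placebo) among all entrants is 0.65/2.70 = 24%. After the reveal it is 27%, 24% or 22% for low, medium or high.

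**Step 5: timing.** The protocol amendment records 675 patients randomized by 29 January 2024. The SAP amendment is dated 17 April 2024, 2 + 29 + 31 + 17 = 79 days later, and week 8 falls nominally 56 days after the first dose. All 675 were therefore past nominal week 8 by then, and those still in the study could have been revealed. This shows opportunity only, not use.

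**Step 6: who is in the primary analysis.** SAP 6.1 says the option to keep enrolling after placebo stopped was not used, and that the efficacy and full analysis sets coincide. Every revealed patient is therefore in the primary analysis.

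**The case against.** The strongest reply is that the blind that matters is intact. All three primary comparisons are a dose against placebo (SAP 6.2), and step 4 shows that the reveal adds almost nothing on that question. The patient's week 8 PANSS, adverse event inquiry and concomitant medication inquiry come before randomization into Period 2 (Protocol 6.9.1), and the reveal later still. That stands, and it limits the point to dose.

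Several stronger readings are tempting, and the documents do not support them.

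- *That intercurrent-event classification in general is exposed.* Much of it concerns the reason for early discontinuation (SAP Table 1). Patients who terminate in Period 1 never get a Period 2 dose to reveal. Those exposed are mainly completers with prohibited antipsychotic use, for whom SAP 1.2.1 sets numerical rules on timing, duration and number of episodes.
- *That dosing-error decisions feed the primary analysis.* They concern the safety analysis set (Protocol 10.2.3; SAP 3.3). The primary analysis follows randomization.
- *That the sponsor's blinded team knows the Period 2 dose, or could compare week 8 PANSS by dose.* The documents name site staff as making the reveal, and unblinded sponsor staff are kept apart from study management during Period 1 (Protocol 6.9). Access is not shown; it is only not excluded.
- *That Protocol 6.9.3 concedes the point.* Its remark, "since patients will be continuing their treatment assignment in Period 2", concerns patients enrolled after placebo is dropped, whose Period 1 arm would be known with certainty. It shows that the link between the two assignments was recognised, but not that the masked re-randomization fails. That option was not used.

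The reveal also follows a process set out in study plans outside these documents, which may restrict access further. That may be so, but the protocol and SAP still claim a full blind and state no such restriction.

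**Conclusion.** For each patient who enters Period 2 and is revealed before the Period 1 lock, two of the four Period 1 arms are excluded with certainty. The Period 1 dose is identified with 75% probability under equal entry, and about 71% to 82% over the assumed entry rates above. A reader might take 75% as a minimum. It is not: the figure falls below 75% whenever placebo patients enter Period 2 more often than patients on that dose. Nor does it apply to every randomized patient, since those who leave in Period 1 are never revealed.

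The statement that Period 1 stays blinded to sponsor, sites and participants until lock is thus not true for dose. Active-versus-placebo status stays essentially masked, so the documents do not support a conclusion that the primary comparisons are compromised. What remains is a property the plan claims and the design lacks, and a missing statement about who may see Period 2 dose data before lock. Both are worth correcting because the correction is cheap.

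**What to change.** 1. In Protocol 4.1 and 6.9 and SAP 2.1 and 2.2, state that after a patient's reveal only placebo versus the revealed dose remains masked.
2. State that until the Period 1 lock, Period 2 dose, dose-adjustment and kit data are kept out of the data sets and listings that the blinded sponsor team uses for SAP changes and intercurrent-event review. The unblinded sponsor staff already provided for in Protocol 6.9 would handle them, with their role extended to the lock.
3. List in the clinical study report any Period 1 value or intercurrent-event classification changed after that patient's reveal.

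Freezing each patient's Period 1 CRF before the reveal may look like the natural remedy, but it cannot reach patients already revealed and is not proposed. The cost is protocol and SAP wording, access settings, one listing, and some extra work for the existing unblinded staff until lock. No dose, visit or analysis changes.
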